## 6 SAFETY ANALYSIS

### 6.1 Extent of Exposure

The extent of exposure to poziotinib will be summarized with descriptive statistics using the following parameters.

- Duration of treatment: days difference between first dose and last dose of poziotinib + 1.
- Number of cycles treated
- Days of treatment administered
- Duration of treatment: number of days from first dose to last dose of poziotinib, which is calculated as (days difference between first dose and last dose +1).

- Relative dose intensity (RDI): the percentage of planned dose that each patient actually received during the study. The planned dose is defined as the dose that would be given if no doses were missed and no dose reductions were made for the number of cycles (28 days per cycle) for the duration of treatment regardless of the number of cycles actually administered. Thus,

$$RDI = 100 * \frac{\text{total dose administered}}{(28 * 16) * \left[ \text{integer of } \left( \frac{\text{days difference between first dose and last dose}}{28} \right) + 1 \right]}$$

- Dose reduction: no reduction and dose reduction to 14mg, 12mg, 10mg and 8mg per cycle and for overall. Temporary dose fluctuation is not considered as dose reduction based on the rules specified in study table shell.

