### 2.1 Study Design and Treatment Plan

This is a Phase 2, open-label, single-arm, multicenter study to evaluate the efficacy and the safety/tolerability of poziotinib in various cohorts. Cohorts 1-4 of the study will enroll up to 174 NSCLC patients previously treated with any systemic therapy (87 patients with EGFR exon 20 insertion mutations and 87 patients with HER2 exon 20 insertion mutations) and up to 140 treatment-naïve NSCLC patients (70 patients with EGFR exon 20 insertion mutations and 70 patients with HER2 exon 20 insertion mutations).

The **Screening** period (**Day -30 to Day -1**) lasts up to approximately 30 days prior to **Cycle 1, Day 1**. Patients must meet all Inclusion/Exclusion Criteria to participate in the study. Eligible patients will provide written Informed Consent prior to undergoing any study procedures.

Each treatment cycle is 28 calendar days in duration. There will be four patient cohorts and eligible patients will be enrolled into each cohort in parallel based on EGFR or HER2 exon 20 mutant status and prior treatment status:

- **Cohort 1:** Previously treated patients with EGFR exon 20 insertion mutation positive metastatic NSCLC
- **Cohort 2:** Previously treated patients with HER2 exon 20 insertion mutation positive metastatic NSCLC
- **Cohort 3:** Treatment naïve patients with EGFR exon 20 insertion mutation positive metastatic NSCLC
- **Cohort 4:** Treatment naïve patients with HER2 exon 20 insertion mutation positive metastatic NSCLC

Toxicity will be assessed based on the grade of the adverse events (AEs) using CTCAE version 4.03.

Poziotinib will be taken orally, once daily (QD) with food and a glass of water at approximately the same time each morning. On **Day 1** of each 28-day cycle, the patient's absolute neutrophil count (ANC) must be  $\geq 1.5 \times 10^9/L$  and platelet count must be  $\geq 100 \times 10^9/L$  before administering poziotinib.

All patients will be treated until 24 months of treatment, disease progression, death, intolerable AEs, or other protocol-specified reason for patient withdrawal.

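### The relative dose intensity denominator counts whole 28-day cycles, so a patient who missed and reduced nothing scores below 100% unless the last dose falls on day 28 of a cycle

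*SAP*

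**What the plan says.** Section 6.1 introduces the measure as "Relative dose intensity (RDI): the percentage of planned dose that each patient actually received during the study". It then fixes the planned dose: "The planned dose is defined as the dose that would be given if no doses were missed and no dose reductions were made", counted "for the number of cycles (28 days per cycle) for the duration of treatment regardless of the number of cycles actually administered". The formula that follows divides the total dose administered by (28 × 16) × [integer of (days difference between first and last dose / 28) + 1].

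The same section defines treatment length in days, and does so twice. One entry reads "Duration of treatment: days difference between first dose and last dose of poziotinib + 1".

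Two other sections bear on the formula. Section 2.1 sets the frequency ("Poziotinib will be taken orally, once daily (QD) with food") and ends treatment at 24 months, progression, death, intolerable adverse events or another withdrawal reason. None of the last four is tied to the end of a cycle. Section 5.5.5 computes average daily dose between scans as total dose divided by total days, with no rounding to cycles.

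**The concern.** Days after a patient has permanently stopped are neither missed doses nor reduced doses. On the SAP's description of planned dose, a patient who took every dose in full up to the last one should score 100%. The formula gives that result only at exact cycle ends. On any other stopping day it adds up to 27 days of dose that the patient was never due to take.

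What is at stake is how the exposure table reads. RDI should show how much of the intended dose was lost to omission and reduction. As written, it also reflects the day of the cycle on which treatment happened to stop. The distortion is always downward and is largest for short treatment, so RDI becomes tied to early progression and early withdrawal. Each cohort is reported separately (Section 3), so a difference in treatment duration between cohorts would show up as an apparent difference in dose intensity.

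**Working it through.** The SAP states no RDI value to reproduce, so the check evaluates its formula directly.

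**Inputs.** Once-daily dosing and a 28-day cycle (Section 2.1). Reference dose of 16 mg, hence 28 × 16 = 448 mg per cycle (Section 6.1 formula). Duration D = days difference + 1 (Section 6.1), so days difference = D − 1.

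**Formula for full adherence.** A patient on 16 mg every day for D days receives 16 × D mg. Then

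RDI = 100 × 16D / {448 × [int((D − 1)/28) + 1]} = 100 × D / (28 × number of cycles entered).

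**Single stopping days.**

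| Last dose on day D | Cycles charged | Calculation | RDI as written |
|---|---|---|---|
| 1 | 1 | 1/28 | 3.6% |
| 14 | 1 | 14/28 | 50.0% |
| 28 | 1 | 28/28 | 100% |
| 29 | 2 | 29/56 | 51.8% |
| 42 | 2 | 42/56 | 75.0% |
| 56 | 2 | 56/56 | 100% |
| 57 | 3 | 57/84 | 67.9% |
| 85 | 4 | 85/112 | 75.9% |
| 113 | 5 | 113/140 | 80.7% |
| 365 | 14 | 365/392 | 93.1% |

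**By cycle of stopping.** The minimum in cycle k falls on its first day: 100 × (28(k − 1) + 1)/(28k). This gives 3.6, 51.8, 67.9, 75.9 and 80.7% for cycles 1 to 5, and 92.6% for cycle 13. If every stopping day in the cycle is equally likely (an assumption), the mean is 100 × (28(k − 1) + 14.5)/(28k), which gives 51.8, 75.9, 83.9 and 87.9% for cycles 1 to 4.

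**Any patient, adherent or not.** Total dose/(448 × cycles) = [total dose/(16 × D)] × [D/(28 × cycles)]. The formula therefore multiplies the day-based RDI by a factor that depends only on the stopping day and never exceeds 1.

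**Confusion with dose reduction.** 16 mg for 42 days is 672 mg; 672/896 = 75.0%. 12 mg, a reduction level listed in Section 6.1, for 56 days is also 672 mg; 672/896 = 75.0%. The first patient lost no dose while on treatment; the second was dosed 25% below the reference throughout.

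**Illustrative averages.** The SAP gives no expected treatment duration. If durations are assumed exponential with a median between 60 and 180 days, mean RDI under perfect adherence runs from 75% (median 60) to 87% (median 180), and between 43% and 18% of these patients fall below 80%. The 80% line is only a marker; the SAP sets no RDI threshold.

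**Reading of the integer function.** Rounding to the nearest whole number instead of truncating does not help: D = 28 then gives 28/56 = 50.0%.

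**After the change.** With 16 × D as the denominator, RDI = 100 × 16D/(16D) = 100% for every D under full adherence.

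**The case against.** The strongest reply is that the formula does what its text says. The definition speaks of a number of cycles at 28 days each, so counting whole cycles was deliberate and is not a slip of arithmetic. That stands. But the same sentence ties the count to the duration of treatment and describes a patient with nothing missed and nothing reduced. A rule that reports such a patient at less than full dose intensity does not measure what the sentence describes.

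A second reply is that RDI is one descriptive item among several. Section 6.1 also reports duration in days, days of treatment administered, and reductions by dose level and cycle, and Section 6.3 covers adverse events leading to discontinuation. A careful reader could separate short treatment from reduced dosing. This also stands and limits the importance of the point. A reader might infer that RDI is the trial's main tolerability measure, or that efficacy conclusions are affected. The SAP supports neither: no test or decision uses RDI, ORR does not depend on it, and the Section 5.5.5 model uses dose over actual days.

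Third, a denominator that ends at the last dose has its own bias. Take a patient who receives 16 mg for 5 days, is held, and then leaves under the Section 4.1 reason of a delay of more than 28 days. The present formula gives 80/448 = 17.9%; the day-based formula gives 100%. The whole-cycle rule counts some of the held days, though only by accident of where the cycle ends. This is a real cost of the change and should be stated openly.

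Finally, scans are scheduled near cycle starts (Section 2.3), so stopping days need not be spread evenly within a cycle. The averages above could move either way; the single-day values do not depend on that assumption.

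**Conclusion.** The point holds. As written, RDI is below 100% for a fully adherent patient on every stopping day except day 28 of a cycle. The bias is downward and falls mostly on patients who stop in the first few cycles. The values by stopping day are exact, given once-daily dosing at the 16 mg reference. The cohort-level averages rest on the assumed durations.

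A reader might infer from the day 1 and day 29 figures that adherent patients in general would be reported at 4% to 52%. That is too strong. Values of 52% or lower occur only for a last dose on days 1 to 14 or day 29, which is about 6% (median 180 days) to 16% (median 60 days) of adherent patients under the exponential assumption. From cycle 3 the floor is 67.9%, and from cycle 5 it is 80.7%.

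Severity is moderate to minor: a descriptive safety summary is misleading, but no inference or trial decision changes.

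**What to change.** In Section 6.1, replace the formula with

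RDI = 100 × total dose administered / [16 mg × (days difference between first and last dose + 1)].

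This keeps the SAP's existing 16 mg reference and its own definition of duration. Prorating the last cycle gives the same result, because 448 × D/28 = 16 × D. Amend the planned-dose sentence so that it refers to days on treatment and not to whole cycles.

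Add a footnote that a dose hold immediately before permanent discontinuation is not counted. Where the date of the discontinuation decision is recorded, a supportive figure could end the denominator on that date for those patients.

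The cost is one formula, one sentence and one footnote in the SAP, plus one derivation in the program. The main figure needs no new data, and the change touches only a summary statistic, not any dose or dosing rule.

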## 6.2 Pharmacokinetics

The PK analysis will be covered in a separate analysis plan.

## 6.3 Adverse Events

An AE is defined as any untoward medical occurrence in a patient or clinical investigation patient, temporally associated with the use of a medicinal product, whether or not considered related to the medicinal product. All AEs that occur from the first dose of study treatment through 35 (±5) days after the last dose of study treatment is administered will be recorded on the AE CRF. From the time the study Informed Consent is signed through the first dose of study drug administration, only serious AEs (SAEs) that are related to study procedures will be recorded.

AEs will be coded using the Medical Dictionary of Regulatory Activities (MedDRA, version 17) and will be classified by MedDRA system organ class (SOC) and preferred term (PT). All AEs will be classified for severity by the Investigator according to the definitions set forth by the Common Terminology Criteria for Adverse Events (CTCAE version 4.03).

All AE tables will be presented with number and percentage of patients. AE listings will include patient ID, gender, age, race, AE verbatim term and preferred term, AE start date and end date, AE duration, CTCAE grade, if the AE is SAE or not, relation to study drug, study drug action, outcome, and if treatment is given.

Only treatment-emergent AEs (TEAE), as defined in **Section 6.3.2**, will be summarized in tables. SAEs reported prior to treatment but after informed consent will only be provided in AE listings.

### 6.3.1 Overall Summary

An overall summary table of TEAEs will be provided. The summary will include any TEAE, TEAE by severity, SAE, TEAE and SAE leading to study drug discontinuation, any treatment-related AE, treatment-related AE by severity, treatment-related SAE, and treatment-related AE leading to study drug discontinuation.

### 6.3.2 Treatment-Emergent Adverse Events

TEAEs are AEs that occur from the first dose of study treatment until 35 (±5) days after the last dose of study treatment. If it cannot be determined whether an AE is treatment-emergent (based on start date or, if the start date is missing then based on the stop date), then the AE will be considered treatment-emergent.

Summary of TEAEs by MedDRA SOC and PT will be presented with any grade and with Grade 3 or 4. Patients who experience more than one type of AE will be counted under each of the corresponding PTs. Patients who experience different episodes of the same AE will be counted only once under the corresponding PT. Similarly, for determination of MedDRA SOC incidences, patients who experience multiple AEs under the same SOC will be counted only once for that SOC. Listing of all TEAEs will also be provided.

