### **6.3.3 Treatment-Related Adverse Events**

Assessment of relatedness to study drug for all AEs will be classified by investigators and reported. “Definitely related”, “probably related” and “possibly related” AEs will be considered as treatment related. An AE will be assigned as treatment-related if the relationship to study drug cannot be determined.

The incidences of treatment-related AEs will be presented by MedDRA SOC and PT with any grade and with Grade 3 or 4.

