### **6.3.4 Serious Adverse Events**

SAEs are defined (21 CFR 312.32, ICH of Technical Requirements for Registration of Pharmaceuticals for Human Use E2A Guideline) as those AEs that meet any of the following criteria:

- Results in death.
- Is life-threatening: ie, any event that, in the opinion of the Investigator, poses an immediate risk of death from that event.
- Requires inpatient hospitalization or prolongation of existing hospitalization (excluding hospitalizations for study therapy, disease-related procedures, or placement of an indwelling catheter, unless associated with other SAEs).
- Results in a persistent or significant disability/incapacity.
- Results in a congenital anomaly/birth defect.
- Includes important medical events that may not be immediately life threatening or result in death or hospitalization but may jeopardize the patient or may require intervention to prevent one of the outcomes listed in this definition.

Listing of all SAEs will be provided. Treatment-emergent SAEs and treatment-related SAEs will be summarized by MedDRA SOC and PT with any grade and with Grade 3 or 4.

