### **6.3.5 Maximum Severity of Adverse Events**

TEAEs and treatment-related AEs will be summarized by MedDRA SOC, PT, and maximum CTCAE severity grade. AEs with a missing severity grade will not be included in these analyses. Patients who experience the same event at more than one severity level will be counted only once under the maximum severity level.

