### **6.3.6 Other Important Adverse Events**

AEs leading to death and study drug discontinuation will be presented in separate listings and the incidence will be summarized in the overall summary of TEAE table.

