### **6.3.7 Adverse Events of Special Interest**

Summary of TEAEs, treatment-related AEs, and SAEs for diarrhea, rash, and stomatitis by MedDRA SOC and PT will be provided in separate tables with any grade and with Grade 3 or 4. Study day of first incidence for diarrhea, rash, and stomatitis will be summarized using median and range.

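### The high-grade adverse-event columns stop at Grade 4, so in four table families a fatal event can count only under any grade

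*SAP*

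**What the plan says.** Section 6.3 has investigators grade all adverse events by CTCAE version 4.03. Four later sections then fix which grades the tables show:

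- Section 6.3.2, treatment-emergent events: "Summary of TEAEs by MedDRA SOC and PT will be presented with any grade and with Grade 3 or 4".
- Section 6.3.3, treatment-related events: "The incidences of treatment-related AEs will be presented by MedDRA SOC and PT with any grade and with Grade 3 or 4".
- Section 6.3.4, serious events: "Treatment-emergent SAEs and treatment-related SAEs will be summarized by MedDRA SOC and PT with any grade and with Grade 3 or 4".
- Section 6.3.7, diarrhea, rash and stomatitis: the summaries "will be provided in separate tables with any grade and with Grade 3 or 4".

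None of the four extends the upper column to Grade 5 or adds a column for it.

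Three other sections report on severity or death. Section 6.3.5 plans: "TEAEs and treatment-related AEs will be summarized by MedDRA SOC, PT, and maximum CTCAE severity grade". Section 6.3.6 states: "AEs leading to death and study drug discontinuation will be presented in separate listings", and places their incidence in the overall summary table. Section 6.3.1 lists that table's contents: "The summary will include any TEAE, TEAE by severity, SAE, TEAE and SAE leading to study drug discontinuation", followed by the treatment-related counterparts, including treatment-related events by severity.

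**The concern.** The SAP does not spell out the CTCAE grades, but Grade 5 of that scale is death. A column limited to Grades 3 and 4 therefore leaves out the worst outcome on the scale. Within such a table, a term whose only high-grade case was fatal looks the same as a term with only mild cases: both show a count under any grade and nothing in the column beside it. This is most awkward in the serious-event tables, because Section 6.3.4 names death as the first criterion for seriousness.

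Safety and tolerability is a secondary objective (Section 1.2.2). Each cohort is reported on its own, and its report may be submitted separately (Section 3). A reader will often take the high-grade column of one of these tables as the summary of serious toxicity for that cohort. Any omission from it can only lower the figure.

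**Working it through.** The SAP has no figure to reproduce here. The check is to follow one patient through the planned tables and then size the effect on a row.

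**1. A patient whose only high-grade event under a term is Grade 5**

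| Planned output | Where this patient appears |
|---|---|
| 6.3.2 treatment-emergent, by class and term | Any grade only |
| 6.3.3 treatment-related, by class and term (if related) | Any grade only |
| 6.3.4 serious, by class and term | Any grade only |
| 6.3.7 special interest (if one of those terms) | Any grade only |
| 6.3.5 maximum grade, by class and term | Grade 5 |
| 6.3.1 overall summary, by-severity rows | Grade 5 |
| 6.3.6 events leading to death | Listing, and incidence in the overall summary |

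**2. Can Section 6.3.5 stand in for the tables it does not name?** It names treatment-emergent and treatment-related events, not serious or special-interest events. Two steps close that gap.

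- Death is a seriousness criterion in Section 6.3.4, so every Grade 5 treatment-emergent event is a serious one. The Grade 5 entries of the 6.3.5 table for treatment-emergent events are therefore the fatal treatment-emergent serious events. The same holds for treatment-related events.
- Section 6.3 tabulates only treatment-emergent events, and Section 6.3.7 works by preferred term. The special-interest terms are therefore rows of the 6.3.5 table.

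One limit remains. Section 6.3.5 omits events with a missing grade, so an ungraded fatal event would be found only through Section 6.3.6, the general listings and the any-grade columns.

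**3. A patient with both a Grade 3 or 4 episode and a fatal episode of the same term.** If any episode qualifies, the patient is counted in the high-grade column. If patients are counted at their maximum grade, the patient is not. Section 6.3.5 states maximum-grade counting for its own tables. Section 6.3.2 says only that repeated episodes count once, so the rule for the other tables is open.

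**4. Size per patient.** The inputs are the planned cohort sizes in Sections 3.2.1 and 3.2.2: 87 for Cohorts 1 and 2, and 70 for Cohorts 3 and 4. The fall in a row's high-grade percentage per affected patient is 100 × 1/n.

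- n = 87: 100 × 1/87 = 1.1 points.
- n = 70: 100 × 1/70 = 1.4 points.

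Section 3.3.1 prints percentages as whole numbers for samples of up to 100. A term with one fatal case and no Grade 3 or 4 case would print 0% where a Grade 3 or higher column would print 1%, in either cohort size.

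**The case against.** The best defence is that the column is labelled Grade 3 or 4 and would report exactly that. The SAP never calls it the severe column. Showing Grades 3 and 4 together and giving Grade 5 elsewhere is a presentation choice, and Grade 5 is given elsewhere by class and term. These are descriptive tables in single-arm cohorts, and no test, population or stopping rule depends on them. All of this stands, and it is why the point is minor. It does not explain why a reader of the serious-event table should need a second table to see its fatal cases.

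Three stronger readings are tempting, and the SAP does not support them.

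- *Fatal events drop out of the safety reporting, or at least out of serious and special-interest reporting by term.* They do not. The Section 6.3.5 tables cover both by the argument in step 2, and Section 6.3.6 adds a listing and an incidence.
- *High-grade toxicity is understated by several points.* That needs several patients with a fatal event under the same term and no qualifying Grade 3 or 4 episode. The SAP gives no number of fatal events, so no total can be defended.
- *Section 6.3.1 contradicts Section 6.3.6 on events leading to death.* Section 6.3.1 says what the table will include and does not say that the list is complete. Section 6.3.6 places the row in that table. Read together, the row is specified, and naming it in 6.3.1 would only be tidier.

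**Conclusion.** The point holds in a limited form. In the four table families of Sections 6.3.2, 6.3.3, 6.3.4 and 6.3.7, the high-grade column read literally omits a patient whose only high-grade event under a term is fatal. The effect runs in one direction and stays within those columns: 1.1 points per affected patient at n = 87 and 1.4 points at n = 70. The number of affected patients is unknown.

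This rests on three assumptions: that the tables are programmed as worded, that Grade 5 denotes death under CTCAE 4.03, and that the safety population of each cohort is close to its planned size. No information is lost overall, so the severity is low. The case for acting is that the correction costs almost nothing.

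**What to change.** In Sections 6.3.2, 6.3.3, 6.3.4 and 6.3.7, do one of the following:

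- replace Grade 3 or 4 with *Grade 3 or higher (3, 4 or 5)*; or
- keep Grade 3 or 4 and add a separate Grade 5 column.

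The first option also makes the open counting rule harmless, since a patient has some event of Grade 3 or higher exactly when the maximum grade is 3 or higher. With the second option, the SAP should state that each patient is counted once, at the maximum grade under the term, so that the columns do not overlap.

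Optionally, name a row for treatment-emergent events leading to death in Section 6.3.1, where Section 6.3.6 already places it.

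The cost is a change to SAP wording and table shells, with no new data. With the first option, high-grade percentages may look slightly worse.
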